10.1.5 Exploratory

If any stool samples assessed via PCR and CCID₅₀ yield a qualifying sample for the deep sequencing and neurovirulence assays (qualification based on the assay input cutoff(s)

provided by the contracted CRO), descriptive analysis of viral sequence heterogeneity will be conducted, as well as descriptive and comparative analysis of neurovirulence assay results to results obtained from samples collected in the Phase IV historical control study.

10.1.6 *Missing Data*

In spite of best efforts to collect complete data for all study subjects, some data will be missing at the end of the trial. The reasons for missing data will be ascertained and appropriate statistical methods will be used to accommodate these absences in the analyses of trial data that minimize potential biases and maximize efficiency conditional on the causes for data being missing. Data values that are identified by quality control procedures to be spurious will not be used in final analyses of trial data.

10.2 DETERMINATION OF SAMPLE SIZE

Groups 1 through 4:

Sample size is chosen here to mirror that of the historical control study, UAM1. The serotype 2 Day 28 seroprotection rate among OPV-vaccinated individuals is expected to be 95% for subjects receiving a single dose of either investigational vaccine or the type 2 Sabin OPV control vaccine (historical control). 77 evaluable subjects per vaccine group are required to achieve 80% power for a test of non-inferiority to the historical control with a type I error rate of $\alpha = 0.025$ and a non-inferiority margin of 10%. 45 subjects are required to have 90% probability of observing at least one occurrence of an adverse event, when the true adverse event rate is 5%. Allowing for a 10% non-evaluability/dropout rate requires 50 subjects for the safety evaluations. For each vaccine candidate, both 1- and 2-dose groups may be used to assess the Day 28 immunogenicity endpoint, providing 100 subjects for the primary immunogenicity comparison. Therefore, 50 subjects will be allocated to each dose group, to also collect adequate safety data for each group, as defined above.

Groups 5 through 7:

Due to observed transient and asymptomatic elevated values of alanine aminotransferase (ALT), aspartate aminotransferase (AST) and creatine kinase (CK) in the first-in-human phase 1 study, UAM4a, conducted in IPV-vaccinated adults in a contained environment, CK, ALT, AST, GGT, bilirubin and albumin have been designated for further evaluation in this study. Data from OPV-primed individuals in study UAM1 suggest the background rate of spurious elevations with the safe mOPV2 vaccine may be approximately 6%. If the true rate with either candidate vaccine is 4 times the expected rate, 44 subjects per group (each vaccine, plus control) would be required to have 80% power to detect a significant increase in the rate (lower one-sided 95% confidence bound for risk difference > 0) relative to the placebo group. If, upon review of interim safety data, the DSMB agrees that a) despite all reasonable efforts, recruitment has stagnated, and b) sufficient data have accrued to satisfy safety objectives relevant to these groups, group sizes can be truncated.

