Exploratory endpoints will include assessment for neurovirulence of shed virus (as measured in animal model(s)) and will also include assessment of the genetic stability of the modified regions of shed virus in a subset of stool samples.

Due to observed transient and asymptomatic elevated values of alanine aminotransferase (ALT), aspartate aminotransferase (AST) and creatine kinase (CK) in the first-in-human phase 1 study, UAM4a, conducted in IPV-vaccinated adults in a contained environment, CK, ALT, AST, GGT, bilirubin and albumin have been designated for further evaluation in this study. Should any anomaly be detected, this can be further explored by additional laboratory testing (e.g. CK subtypes, electrophoresis, auto-antibodies (e.g. ANA, AMA, LKM-1, SLA/LP, other viral pathogens)

Statistical Methods:**Sample size****Groups 1 through 4:**

Sample size is chosen here to mirror that of the historical control study, UAM1. The serotype 2 Day 28 seroprotection rate among OPV-vaccinated individuals is expected to be 95% for subjects receiving a single dose of either investigational vaccine or the type 2 Sabin OPV control vaccine (historical control). 77 evaluable subjects per vaccine group are required to achieve 80% power for a test of non-inferiority to the historical control with a type I error rate of $\alpha = 0.025$ and a non-inferiority margin of 10%. 45 subjects are required to have 90% probability of observing at least one occurrence of an adverse event, when the true adverse event rate is 5%. Allowing for a 10% non-evaluability/dropout rate requires 50 subjects for the safety evaluations. For each vaccine candidate, both 1- and 2-dose groups may be used to assess the Day 28 immunogenicity endpoint, providing 100 subjects for the primary immunogenicity comparison. Therefore, 50 subjects will be allocated to each dose group, to also collect adequate safety data for each group, as defined above.

Groups 5 through 7:

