Non-inferiority comparisons will be conducted by computing the difference in endpoint between each candidate vaccine and the UAM1 Sabin 2 control (novel minus comparator), with corresponding two-sided $\alpha = 0.05$ confidence intervals, with inference drawn from comparison of the lower confidence limit to the non-inferiority margin.

Score-based confidence intervals will be used for binary comparisons, asymptotic normal-based methods will be used for GMTs, and bootstrap methods will be used for median titers and other continuous endpoints.

Immunogenicity comparisons will be based on the combined data from each site in this study compared to the single-site data from the historical control study, UAM1. In the event that between-site comparisons within this study indicate that significant differences in outcomes (two-sided tests for differences at $\alpha = 0.05$) exist between sites, additional

comparisons for all immunogenicity endpoints will be added to compare vaccine candidates using only data at the site in common between both studies. Comparisons of binary endpoints between sites in this study will be based on 95% two-sided score intervals for the difference; comparison of continuous endpoints will be based in two-sided 95% bootstrap-based confidence intervals for the difference in medians (median titer), or normal-based methods (for GMTs). Differences between sites will be indicated by a nominal value (percent/median/mean difference of zero) excluded from the confidence interval coverage region.

Viral Shedding

For each group (excluding Group 7), site, and time point, viral shedding positivity and concentration will be summarized. For each subject, a viral shedding index will be calculated as the average of \log_{10} -transformed values of viral concentration in stool samples as determined using quantitative PCR (viral identity) and CCID₅₀ (titer) from select stool samples taken following each vaccine dose, and this index will be summarized by group. The time to cessation of shedding, defined as the time interval between administration of vaccine and the last day of shedding positivity prior to cessation, will be assessed with Kaplan-Meier methods to describe and compare the duration of shedding.

Descriptive analysis and plots of the reverse cumulative distribution of the viral shedding index will be generated.

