Seroprotection rates at baseline will be accompanied by a two-sided Miettinen and Nurminen 95% confidence interval for the difference for Groups 1 & 2 combined as well as Groups 3 & 4 combined vs the UAM1 control (Group 1 & 2 combined). Similarly, comparisons of baseline seroprotection rate between Group 5 vs 7 and Group 6 vs 7 will be conducted. Comparison of baseline GMTs among these same groups will be conducted by computing the GMT ratio and corresponding two-sided 95% confidence interval obtained from modeling the \log_2 NAb titer as a function of group using SAS PROC LIFEREG, as described above. For IPV-vaccinated subjects, this will include a fixed effect for study site, utilizing SAS LSMEANS for pairwise comparisons. For by-site summaries, comparisons will only be available at the site in common between UAM4 and UAM1.

Comparative Analysis

The primary immunogenicity endpoint, seroprotection after a single dose of each vaccine candidate in OPV-vaccinated subjects, will be formally compared to the corresponding endpoint from UAM1 via a non-inferiority test of each of the novel candidates to the UAM1 Sabin 2 control, each using one-sided $\alpha = 0.025$ and a non-inferiority margin of -10%.

Secondary endpoints will be compared to corresponding endpoints from UAM1 in the same manner, using one-sided $\alpha = 0.025$ and considering margins of -10% for binary endpoints (seroconversion), and 2/3 for median antibody titer and GMT ratios. Non-inferiority margins for these secondary endpoints are not selected based on any specific criteria and are simply intended as benchmarks for unpowered comparisons.

In each case, non-inferiority comparisons will be conducted by computing the difference/ratio in endpoint between each candidate vaccine and the UAM1 Sabin 2 control (novel minus comparator), with corresponding two-sided $\alpha = 0.05$ confidence intervals, and comparing the lower confidence limit to the non-inferiority margin. Miettinen and Nurminen confidence intervals will be used for binary comparisons, asymptotic normal-based methods will be used for GMTs as described above using SAS PROC LIFEREG and incorporating a covariate for the baseline \log_2 NAb level, and bootstrap methods will be used for median titers and other continuous endpoints.

Immunogenicity among IPV-vaccinated subjects (Groups 5 through 7) will be summarized descriptively but will not be compared between groups.

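### The stated 77 evaluable subjects for 80% power do not fit the planned score interval: exact power at 77 per arm is 71%, and about 95 per arm are needed

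*Protocol*

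**What the plan says.** Protocol 10.2 (Groups 1 through 4), repeated in the synopsis, says that "77 evaluable subjects per vaccine group are required to achieve 80% power for a test of non-inferiority to the historical control". The calculation uses a one-sided type I error of 0.025 and a margin of 10 percentage points. Day 28 seroprotection "is expected to be 95% for subjects receiving a single dose of either investigational vaccine or the type 2 Sabin OPV control vaccine". No formula or test is named for the calculation. Each candidate has two dose groups of 50, which gives 100 subjects for the Day 28 comparison. The UAM1 control was also planned at 100, and its synopsis (Protocol Appendix 3) carries the same figure of 77.

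The analysis method is specified. Protocol 10.1.3 states: "Score-based confidence intervals will be used for binary comparisons". SAP 6.6.1 is more precise: "Miettinen and Nurminen confidence intervals will be used for binary comparisons". Non-inferiority is judged by "comparing the lower confidence limit to the non-inferiority margin", using a two-sided 95% interval and a margin of −10%.

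**The concern.** With rates near 95%, the choice of interval has a large effect on power. The Wald interval takes its variance from the observed proportions. The score interval takes it from proportions constrained to differ by the margin, roughly 87% against 97% here, and that variance is larger. A sample size found with the first method therefore overstates the power of the second.

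This is the only formally tested primary immunogenicity hypothesis, and its primary analysis is per-protocol. A reader of Protocol 10.2 would conclude that 100 enrolled against 77 needed leaves 23 subjects per candidate to spare. Some losses are foreseeable. Hepatitis, HIV and IgA results come from blood drawn on Day 0, the day of first vaccination, and an abnormal result removes the subject from the per-protocol population (Protocol 5.3). Withdrawn subjects are not replaced (Protocol 9.2.1).

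**Working it through.** **Inputs**

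- True rates 95% and 95%, margin 0.10, one-sided alpha 0.025, target power 80%: Protocol 10.2.
- Test: lower limit of the two-sided 95% Miettinen–Nurminen interval above −10%: SAP 6.6.1.
- Planned sizes: 100 per candidate (Protocol 10.2) and 100 in UAM1 (Protocol Appendix 3).
- Loss: 10%. Protocol 10.2 gives this for the safety evaluations. Applying it to the immunogenicity comparison, to get 100 × 0.9 = 90 evaluable, is an assumption.

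**Step 1: the plan's own figure**

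The unpooled normal formula is

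n = (1.960 + 0.8416)² × (2 × 0.95 × 0.05) / 0.10² = 7.849 × 0.095 / 0.01 = 74.6, so 75 per arm.

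At n = 77 the standard error is √(0.095/77) = 0.0351. Power is Φ(0.10/0.0351 − 1.960) = Φ(0.887) = 81.2%. Exact enumeration of the Wald rule at 77 gives 80.9%. The stated 77 is therefore consistent with a Wald-type calculation, to within two subjects.

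**Step 2: the asymptotic size for a score test**

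Under the constraint of a −10-point difference, the restricted rates (Farrington–Manning) are 0.8703 and 0.9703. The variance sum is 0.8703 × 0.1297 + 0.9703 × 0.0297 = 0.1417, compared with 0.095 in Step 1. Then

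n = (1.960 × √0.1417 + 0.8416 × √0.095)² / 0.01 = 99.4, so 100 per arm.

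**Step 3: exact power of the planned test**

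All pairs (X₁, X₂) were enumerated, with each count binomial with probability 0.95. Non-inferiority is declared when

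(p̂₁ − p̂₂ + 0.10) / √{[p̃₁(1 − p̃₁)/n₁ + p̃₂(1 − p̃₂)/n₂] × N/(N − 1)} > 1.960,

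where p̃₁ and p̃₂ are the restricted maximum-likelihood estimates and N = n₁ + n₂.

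| Candidate / control evaluable | Exact Miettinen–Nurminen power |
|---|---|
| 77 / 77 | 71.1% |
| 77 / 100 | 74.7% |
| 90 / 90 | 79.4% |
| 90 / 100 | 78.9% |
| 94 / 94 | 78.3% |
| 95 / 95 | 81.4% |
| 95 / 100 | 79.5% |
| 100 / 100 | 83.2% |

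Exact power moves in a sawtooth as n changes, so a single crossing of 80% is not enough. With equal arms, 95 is the first size to reach 80%, and power stays at or above 80% for every size from 95 to 130. A separate numerical maximisation of the restricted likelihood gave the same power at 77 and 95.

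**Step 4: other score intervals**

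The protocol says only that the interval is score-based. Without the N/(N − 1) factor, power at 77 is 71.1% and 95 per arm are needed. With Newcombe's hybrid score interval, the figures are 71.1% and 93. No common score version supports 77.

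**Step 5: type I error at the margin**

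At true rates of 85% and 95% with 77 per arm, the exact one-sided error is 3.3% for the Wald rule and 2.3% for Miettinen–Nurminen. Part of the Wald rule's extra power comes from exceeding the stated 0.025.

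**Step 6: the neighbouring calculation**

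For the IPV groups, 44 per group at 6% against 4 × 6% = 24%, with a one-sided 95% Miettinen–Nurminen bound, gives 79.7%. That is close to the stated 80%. The two sample sizes in this section thus appear to rest on different methods, although the protocol does not say which were used.

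**The case against.** The strongest reply is that 77 contains no slip in calculation and that nothing was built on it. It agrees with a standard formula, the protocol says the size was chosen to mirror UAM1, and the 50 per dose group came from the safety calculation. The planned 100 against 100 has 83% power under the planned test. All of this stands. It limits the consequence, but the sentence still claims a power that the specified test does not have.

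The reserve of 23 is a reader's inference, and the 10% loss is stated for safety only. Both points are fair, and 90 evaluable is labelled an assumption here. The per-protocol rules also limit losses, because subjects in Groups 2 and 4 who miss the second dose keep their Day 28 data. The 0.6-point shortfall at 90 per arm is small beside the uncertainty in the assumed rate: power there is 74.1% if both rates are 94%, and 84.9% if both are 96%.

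UAM1 was finished before this trial, so power could be conditioned on its result. With 77 candidates at a true 95%, conditional power is 81.3% if UAM1 observed 95/100 and 65.9% if it observed 96 or 97/100. The documents do not give the UAM1 rate, and Protocol 10.2 describes an unconditional calculation, so this does not restore the stated figure.

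Finally, 95 applies to equal arms; 95 against 100 gives 79.5%. That is a reason to say about 95.

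**Conclusion.** The concern holds. For the test the plan specifies, 77 evaluable subjects per arm give 71% power, about 9 points below the stated 80%. About 95 per arm are needed, 18 more than stated. The fault is a mismatch between the method used for sizing and the method used for analysis. The planned comparison is adequately powered at 83% if everyone is evaluable, and falls just short at 79% if 10% are lost. The reserve below 100 is about 5 subjects per arm rather than 23. These figures rest on the protocol's own assumption of 95% seroprotection in both studies and treat both arms as random samples. The statement should be corrected, but the design is not undermined.

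**What to change.** In Protocol 10.2 and the synopsis, replace the sentence about 77 subjects with wording such as:

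> Assuming 95% seroprotection in both studies, a margin of −10 percentage points and one-sided alpha 0.025, the Miettinen–Nurminen comparison has about 83% power with 100 evaluable subjects in each of the candidate and UAM1 arms, and about 79% with 90 in each. About 95 evaluable subjects per arm are needed for 80%.

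The SAP has no sample-size section. If the protocol is closed to amendment, the statement can go in SAP Section 7 (Differences from the protocol) or in the clinical study report.

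The cost is one sentence and a less favourable statement of how many exclusions the comparison can absorb. Enrolment, the analysis method and the decision rule are unchanged.

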4. STUDY DESIGN

4.1 OVERVIEW OF STUDY DESIGN

This will be a multicenter, partial blind, placebo-controlled, randomized study in 200 healthy OPV-vaccinated adults and **in 48 to 132** healthy IPV-only vaccinated adults (18 to 50 years), as follows:

- 50 OPV-vaccinated adults to receive 1 dose of nOPV2 candidate 1 (Group 1);
- 50 OPV-vaccinated adults to receive 2 doses of nOPV2 candidate 1 (Group 2), administered 28 days apart;
- 50 OPV-vaccinated adults to receive 1 dose of nOPV2 candidate 2 (Group 3);
- 50 OPV-vaccinated adults to receive 2 doses of nOPV2 candidate 2 (Group 4), administered 28 days apart;
- **16 to 44** IPV-only vaccinated adults to receive 2 doses of nOPV2 candidate 1 (Group 5), administered 28 days apart;
- **16 to 44** IPV-only vaccinated adults to receive 2 doses of nOPV2 candidate 2 (Group 6), administered 28 days apart.
- **16 to 44** IPV-only vaccinated adults to receive 2 doses of placebo (Group 7), administered 28 days apart.

Groups will be enrolled sequentially such that subjects receiving candidate 2 will be enrolled first (IPV and OPV groups simultaneously), followed by subjects receiving candidate 1. IPV-only vaccinated adults will be randomized 2:1 to candidate 2 (Group 6) or placebo (Group 7), respectively, until all **16 to 44** Group 6 subjects are enrolled, after which randomization 2:1 to candidate 1 or placebo will commence for Groups 5 and 7. For OPV-vaccinated subjects, randomization to Groups 1 and 2 to receive candidate 1 will ensue following complete randomized enrollment of subjects to Groups 3 and 4. In all cases, block randomization will be used to ensure balanced randomization across time.

The DSMB has established stopping rules for safety prior to study start which will be continuously assessed. **The DSMB will also monitor study enrollment, particularly for IPV-vaccinated subjects, and recommend truncation and/or closure of study groups if enrollment stagnates and when current enrollment is considered sufficient to meet study objectives and no safety signals occurred.** The minimum number of IPV-vaccinated subjects agreed on by DSMB per vaccine candidate is 24. With a randomization of 2:1 for placebo the minimum study cohort size for Groups 5, 6 and 7 will be 16. In case of safety signals the DSMB reserves the right to reverse the truncated enrollment.

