3.7 Data Monitoring

An independent Data and Safety Monitoring Board (DSMB) is charged with monitoring the benefit-risk and data integrity of this trial, to inform the sponsor about recommendations for future clinical trial phases.

The DSMB has established stopping rules for safety prior to study start, which are continuously assessed. The DSMB will also monitor study enrollment, particularly for IPV-vaccinated subjects, and recommend truncation and/or closure of study groups if enrollment stagnates and when current enrollment is considered sufficient to meet study objectives and no safety signals occurred. The minimum number of IPV-vaccinated subjects agreed on by DSMB per candidate vaccine is 24. With a randomization of 2:1 for placebo the minimum study cohort size for Groups 5, 6 and 7 will be 16. In case of safety signals the DSMB reserves the right to reverse the truncated enrollment. The structure and content of the DSMB reports will agree between the sponsor and the DSMB, independent of this analysis.

4 Analysis Populations

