5.2 Timing of Analysis

A final analysis of all data will be performed when all data are collected and the database is locked, following a blinded (for IPV-vaccinated subjects) review of criteria for membership in the per-protocol population. The same principles for deviation classification applied to subjects from study UAM1, documented in the data review meeting report and common between UAM1 and UAM4 protocols, will be used here.

Within background vaccination cohort (OPV vs IPV), enrollment in this study was sequential, with respect to candidate. A pre-scheduled unblinded DSMB safety review of data from OPV-vaccinated (n=100) and IPV-vaccinated subjects in Group 3, 4, 6, and 7 (receiving candidate 2) was held following accumulation of 14 days post-first-dose safety data on 24 IPV-vaccinated subjects (randomized 2:1, candidate 2:placebo), to enable age de-escalation in a subsequent study in children and infants. A similar unblinded DSMB safety review was held with updated data to include 14 day post-first-dose safety data from 26 additional subjects receiving candidate 1 or placebo (Groups 1, 2, 5, and 7), to enable age de-escalation in the subsequent phase II study with candidate 1.

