6.5.1 Primary Safety Endpoints

- Solicited adverse events:
 - Serious/severe solicited adverse events will be summarized by group, by post-vaccination time period as well as overall (under maximum severity), and by term by post-vaccination time period as well as overall (under maximum severity), as well as listed.
- Unsolicited adverse events:
 - Serious/severe unsolicited AEs will be summarized by group, maximum causality and by class (serious vs severe) under maximum causality, by post-vaccination

time period (prior to dose 2 vs following dose 2) as well as overall, and reasons for SAE classification (wherever such subcategories are relevant), as well as by SOC and PT among serious events only (and among those serious and related), and among severe events only (and among those severe and related). These events will also be listed.

- Listings will be prepared for those subjects who died or withdrew from the study due to an AE.

Two-sided p-values from the Fisher exact test of the number of subjects with an event will be presented for:

- Severe solicited events (overall, and by event term)
- Any serious unsolicited event
- Any serious and related unsolicited event
- Any severe unsolicited event
- Any severe and related unsolicited event

These comparisons will be conducted for the following groups:

- UAM4 Groups 1 & 2 vs UAM1 Groups 1 & 2
 - Post-dose-1 and overall, TVP
- UAM4 Group 2 vs UAM1 Group 2
 - Post-dose-2, TVP subjects who received both doses
- UAM4 Groups 3 & 4 vs UAM1 Groups 1 & 2
 - Post-dose-1 and overall, TVP
- UAM4 Group 4 vs UAM1 Group 2
 - Post-dose-2, TVP subjects who received both doses
- UAM4 Group 5 vs UAM4 Group 7
 - Post-dose-1, post-dose-2, and overall, TVP
- UAM4 Group 6 vs UAM4 Group 7
 - Post-dose-1, post-dose-2, and overall, TVP

Comparisons for both solicited and unsolicited events will be conducted separately for post-dose-1 and post-dose 2, as well as following any dose. Comparisons involving post-dose-2 data will include only subjects receiving both doses.

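### Groups 5 to 7: the only stated power (80%) belongs to 44 per group, but the amended design permits 16, where power for the same target is about 43%

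*Protocol*

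**What the plan says.** Protocol 10.2 (Groups 5 through 7), repeated in the synopsis, sizes the IPV groups on enzyme elevations. It takes a background from UAM1, where "the background rate of spurious elevations with the safe mOPV2 vaccine may be approximately 6"%, and a target effect: "If the true rate with either candidate vaccine is 4 times the expected rate". The success criterion is "lower one-sided 95% confidence bound for risk difference > 0", and the result is that "44 subjects per group (each vaccine, plus control) would be required to have 80% power to detect a significant increase in the rate".

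Protocol 4.1 now gives each of Groups 5, 6 and 7 a range of 16 to 44: "With a randomization of 2:1 for placebo the minimum study cohort size for Groups 5, 6 and 7 will be 16". The synopsis, Protocol 6.6 and SAP 3.2, 3.3 and 3.7 carry the same range or minimum. Under SAP 3.7 the DSMB may "recommend truncation and/or closure of study groups if enrollment stagnates and when current enrollment is considered sufficient to meet study objectives", provided also that no safety signal has occurred, and it may reverse a truncation if one appears. Protocol 10.2 adds that recruitment must have stagnated despite all reasonable efforts.

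SAP 6.5.2 analyses ALT, AST, CK, GGT, bilirubin and albumin with a two-sided 90% Miettinen-Nurminen interval for the risk difference of Group 5 or 6 against Group 7. For serious and severe adverse events, SAP 6.5.1 says: "Two-sided p-values from the Fisher exact test of the number of subjects with an event will be presented for" a list of event categories. No risk-difference interval is specified there.

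The SAP has no sample-size section. Its list of differences from the protocol mentions only fold-rise summaries.

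**The concern.** The sample-size statement was left unchanged when the permitted group size was widened to 16–44. The only power in either document therefore describes the top of the range, and a reader has nothing by which to judge a trial that closes lower down.

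This matters because the placebo group was added to answer a specific question. Protocol 1.3.1 says that, without a control group in phase 1, a relation between the enzyme changes and the vaccine could not be ruled out. If the groups close near the minimum and no significant difference from placebo is seen, the result may be taken as reassurance backed by 80% power when the actual power for the planning target was about half that.

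The primary severe-event comparison is also affected. Under Protocol 11.2, laboratory values above grade 1 are automatically recorded as adverse events, so severe enzyme elevations enter that comparison. There the plan gives a p-value but no interval for the difference from placebo.

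**Working it through.** **Inputs.** Placebo rate 0.06 and candidate rate 4 × 0.06 = 0.24, so a difference of 0.18 (Protocol 10.2). One-sided 5%, equivalent to the lower limit of the SAP's two-sided 90% Miettinen-Nurminen interval lying above 0 (Protocol 10.2, SAP 6.5.2). Group sizes 44 and 16 (Protocol 10.2, 4.1). No dropout allowance is stated for these groups, so sizes are taken as evaluable. At the minimum, each candidate contributes 24 subjects at 2:1, that is 16 candidate and 8 placebo; the two stages give 8 + 8 = 16 in Group 7.

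**Reproducing the plan's figure.** The unpooled normal formula gives

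n = [0.06 × 0.94 + 0.24 × 0.76] × (1.645 + 0.842)² / 0.18² = 0.2388 × 6.183 / 0.0324 = 45.6,

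within two subjects of 44. Exact enumeration of the two binomials with the Miettinen-Nurminen statistic gives 79.7% power at 44 per group. The arcsine approximation gives 79.9%. The stated 44 and 80% are sound.

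**Same calculation at the minimum.** The statistic at a difference of 0 is

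z = (x₁/n − x₀/n) / √[p̄(1 − p̄)(2/n) × N/(N − 1)], with p̄ the pooled proportion and N = 2n,

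and the criterion is met when z > 1.645. At n = 16:

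| Placebo events x₀ | Candidate events needed | P(x₀) at 6% | P(enough) at 24% | Product |
|---|---|---|---|---|
| 0 | 3 or more | 0.3716 | 0.7768 | 0.2886 |
| 1 | 5 or more | 0.3795 | 0.3341 | 0.1268 |
| 2 | 7 or more | 0.1817 | 0.0657 | 0.0119 |
| 3 | 8 or more | 0.0541 | 0.0214 | 0.0012 |

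Higher placebo counts add almost nothing. The total is 0.429. As a check, the unpooled normal formula gives 0.18/√(0.2388/16) = 1.473, and Φ(1.473 − 1.645) = 43.2%. Across the pooled normal, unpooled normal, arcsine, exact score and exact Wald versions, the range is 41.1% to 44.6%.

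**Power by realised size** (exact, 24% against 6%, equal groups):

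| Per group | Power |
|---|---|
| 44 | 79.7% |
| 32 | 66.8% |
| 24 | 57.8% |
| 16 | 42.9% |

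**What 16 per group can detect.** Solving the exact power for 80% gives a candidate rate of about 41% against 6%, or 0.41/0.06 ≈ 6.8 times background (the pooled normal formula gives 42%, about 7 times). At 50% against 6%, exact power is 91%.

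**What a result at 16 per group would look like** (90% Miettinen-Nurminen interval):
- 4/16 against 1/16 (25% against 6%, almost exactly the planning effect): −3 to +41 percentage points, so the criterion is not met.
- 1/16 against 1/16 (no observed difference): −19 to +19 points, which does not exclude the 18-point target.

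**Severe adverse events.** At 16 per group, two-sided Fisher gives p = 0.101 for 4 against 0 and p = 0.043 for 5 against 0. A p-value above 0.05 therefore says little about how large a difference remains possible; an interval would show it.

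**The case against.** The strongest reply is that nothing in the protocol is false. It says what 44 per group delivers and nowhere claims 80% at 16. That stands: a reader might infer an arithmetic error, and there is none.

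Truncation is also guarded. It needs stagnated recruitment, a DSMB judgement of sufficiency and no safety signal, and it can be reversed. Sixteen is a floor, not a forecast. Nor do the documents define sufficiency as meeting the 24%-against-6% criterion, so it would go too far to say that the DSMB rule contradicts the sample-size section.

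A reader might further infer that the minimum size cannot address the phase 1 finding at all. The documents do not support this. Protocol 1.3.1 reports severe CK elevations in half of the phase 1 participants, and against the plan's 6% background an effect that large has about 91% power at 16 per group. Severe AST elevations were much rarer (2 of 30), so the weakness concerns moderate increases.

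Two other inferences should be resisted. SAP 5.2 describes a DSMB review on "24 IPV-vaccinated subjects (randomized 2:1, candidate 2:placebo"), which suggests 16 against 8, with power of about 21%. That was an interim safety review; the planned final comparison uses all of Group 7. And the Fisher tests are for serious and severe adverse events, for which no power was claimed; they are not a weaker form of the powered laboratory comparison.

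Finally, safety is described as descriptive, and the laboratory intervals will show their own width. This reduces the risk of misreading, but it does not supply the missing power statement and does not cover SAP 6.5.1.

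**Conclusion.** The concern holds as a disclosure gap: a stated power that is not delivered across the permitted sizes. For the plan's own target, power falls from 79.7% at 44 per group to 42.9% at 16, so at the minimum a true fourfold increase would be missed about 57% of the time (100 − 42.9).

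This rests on the protocol's 6% and 24%, one-sided 5%, the Miettinen-Nurminen method, each candidate compared with the whole of Group 7, and group sizes taken as evaluable. The result barely depends on the choice between the score, Wald and normal methods (41% to 45%).

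It should be fixed because it governs how the placebo-controlled safety results may be read. It does not invalidate the design. The DSMB reviews in SAP 5.2 are described as already held, so the value of the change lies in interpretation and reporting.

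**What to change.** 1. In Protocol 10.2, the synopsis and the SAP, replace the single figure with power by realised group size for 24% against 6% (44: 80%; 32: 67%; 24: 58%; 16: 43%), and give the rate detectable with 80% power at 16 per group (about 41% against 6%).
2. State in the SAP that, at truncated size, a non-significant laboratory difference from placebo will be interpreted from the upper limit of the 90% interval and will not be reported as absence of an effect.
3. In SAP 6.5.1, for the severe-event comparisons of Groups 5 and 6 with Group 7, present the risk difference with the 90% Miettinen-Nurminen interval already used in SAP 6.5.2, beside the Fisher p-value.

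The cost is a few sentences, one extra table column and a less favourable stated power. No subjects are added, and the DSMB's truncation rule is unchanged.
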